CLINICAL STUDY PROTOCOL

Understanding Shared Decision-Making in Lung Cancer Screening (DECIDE)

Protocol Version

10.31.2022

version 2

Please note the data for this study has already been collected at my prior institution and the only activity occurring at present is data analysis.

Study Personnel

PI: [name], APRN, ANP-C, FAAN, Director

Cancer Prevention Precision Control Institute at the Center for Discovery & Innovation,

[contact]

Sub-I(s): n/a

Statistical support (if applicable): [name] (Indiana University); [name] (Indiana University)

Protocol Development support (if applicable): Name, Title

Name and information of sponsor: National Cancer Institute, Grant #R01CA222090

Research Locations (all non-HMH locations):

Kaiser Permanente Washington Health Research Institute

[name]

Abbreviations

Abbreviation	Explanation
SDM	Shared Decision Making
LCS	Lung Cancer Screening
LDCT	Low-dose computed tomography
KPWA	Kaiser Permanente Washington

Revision History

Revision #	Version Date	Summary of Changes	Consent Change?

Summary

Please note the data for this study has already been collected at my prior institution and the only activity occurring at present is data analysis.

Study Title	Understanding Shared Decision-Making in Lung Cancer Screening (DECIDE Study)
Study Design	Cross-sectional, survey
Primary Objective	
1) Decision quality,2) Lung cancer screening completion, and3) Advances in stage of adoption for smoking cessation among individuals who currently smoke
Secondary Objective(s)	n/a
Research Intervention(s)	n/a
Study Population	Adults aged 55-80 years who currently smoke or quit within the past 15 years with a 30 pack-year tobacco smoking history
Sample Size	552
Study Duration for individual participants	6 months

1 – Introduction

Our long-term goal is to develop the next generation of decision support tools, including alternative communication strategies, for clinicians and patients to use for lung cancer screening decisions.

This project specifically seeks to identify the components of patient-clinician discussions about lung cancer screening that contribute to high quality decisions and subsequent important behavioral outcomes (screening completion among patients who decide to screen; stage-of-readiness advancement for smoking cessation among current smokers).

Our central hypothesis was that patients who perceive lung cancer screening discussions with their clinician as shared/mutual will have positive decisional and behavioral outcomes. The behavioral outcomes we are evaluating are consistent

with recent findings linking lung cancer screening with improved smoking cessation rates.

We are examining clinician and patient factors simultaneously by collecting patient and clinician survey data and integrating it with patient EHR data.

2 – Background

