3.3. Primary Objective

Aim 1. Use survey and EHR data to identify clinician factors that predict: a) patient-perceived lung cancer screening decision quality; b) screening completion among patients deciding to screen; and c) stage of readiness for smoking cessation among current smokers. *Hypothesis 1: Increased clinician knowledge, positive attitude toward lung cancer screening, positive attitude toward shared decision making (SDM), decreased clinician perceived barriers, and high lung cancer screening referral propensity predict higher decision quality, screening completion, and advances in stage of readiness for cessation.*

Aim 2. Use survey and EHR data to identify patient factors that predict: a) patient-perceived lung cancer screening decision quality; b) screening completion among patients deciding to screen; and c) stage of readiness for smoking cessation among current smokers. *Hypothesis 2: Patient-perceived stigma and medical mistrust predict decreased decision quality, screening completion, and advances in stage of readiness for cessation.*

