3.4. Primary Outcome Variable(s)

a) patient-perceived lung cancer screening decision quality; b) screening completion among patients deciding to screen; and c) stage of readiness for smoking cessation among current smokers

4 - Study Design

Please note the data for this study has already been collected at my prior institution and the only activity occurring at present is data analysis. The following is offered for context:

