4.1 General Design

DECIDE is a descriptive, observational study that includes two populations:

1. KPWA primary care providers (PCP - MDs, DOs, PAs and ARNPs), who have documented, in EPIC, at least one lung cancer screening SDM conversation with an eligible KPWA patient.
2. KPWA patients who have recently engaged in a documented LCS SDM conversation with a KPWA PCP.

Both populations were invited to participate in a survey (two different surveys for the two different populations), regarding their opinions about and experiences with the LCS SDM process. Prospective LCS-related clinical data about the patient participants were collected for 12 subsequent months after they completed the study survey to determine whether they screen, the outcome of their screening and any use of smoking cessation services.

Data from the surveys and electronic medical records will be used to determine where improvements can be made in the SDM for LCS space and to help work toward the goal of developing revised or new tools for this process.

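### The third primary outcome is hypothesised as an advance in cessation readiness but defined as a level, so as defined it supports only an association with level

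*Combined protocol and SAP*

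**What the plan says.** The smoking outcome is one of three primary outcomes, and the document describes it in two ways.

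*As change.* The Summary objective is "Advances in stage of adoption for smoking cessation among individuals who currently smoke". The Introduction and section 3.1 refer to "stage-of-readiness advancement for smoking cessation among current smokers". In section 3.3, Hypothesis 1 ends with "high lung cancer screening referral propensity predict higher decision quality, screening completion, and advances in stage of readiness for cessation", and Hypothesis 2 reads "Patient-perceived stigma and medical mistrust predict decreased decision quality, screening completion, and advances in stage of readiness for cessation".

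*As a level.* Section 3.4 gives the primary outcome variable as "stage of readiness for smoking cessation among current smokers", and Aims 1c and 2c in section 3.3 use the same words. The power paragraph in section 5 also names the stage, with no mention of movement. Table 2 (section 5.5) lists it as stage of readiness, source survey, instrument a one-item Contemplation Ladder, with no assessment time.

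*Design and timing.* The Summary calls the study a cross-sectional survey and gives 6 months under "Study Duration for individual participants". Section 4.1 describes "two different surveys for the two different populations", then 12 months of clinical data on patients after their survey, "to determine whether they screen, the outcome of their screening and any use of smoking cessation services". Section 4.1.1 adds one follow-up point 6 months after the screening discussion and does not say what was collected then.

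*Analysis.* Section 5 models the continuous outcomes of Aims 1 and 2 with a linear mixed model and a random intercept for clinician.

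**The concern.** An advance is movement from one rung to a higher one. A stage is a position at one time. A smoker who was already on a high rung before any screening discussion scores the same as one who moved there afterwards, so a predictor can be related to position without being related to movement.

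What is at stake is the conclusion. Suppose section 3.4 is followed as written and, say, lower stigma goes with a higher rung. That is a valid finding about level. Hypothesis 2, however, is worded about advances, and the natural write-up would report the result as support for it. Readers would then take a cross-sectional association as evidence that readiness moved. The same applies to the clinician factors in Hypothesis 1.

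**Working it through.** The point is one of definition, so the check is to set the texts side by side and see whether any of them closes the gap.

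**1. Wording of the outcome**

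| Place | Change or level |
|---|---|
| Summary, Primary Objective | change |
| Introduction; section 3.1 | change |
| Section 3.3, Hypotheses 1 and 2 | change |
| Section 3.3, Aims 1c and 2c | level |
| Section 3.4, primary outcome variable | level |
| Section 5, power paragraph | level |
| Section 5.5, Table 2 | level |

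Within section 3.3 each aim names a level and its own hypothesis names a change.

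**2. Is a second ladder value described?** No. Three places bear on it.

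- Table 2 gives the ladder's source as the survey, and section 4.1 describes one survey for patients.
- The follow-up point in section 4.1.1 falls 6 months after the discussion, and its content is not stated.
- The clinical data in section 4.1 run for 12 months from the survey. That is a different starting point and a different length, so the list of items there does not settle what the 6-month point collected.

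A repeat ladder is therefore neither stated nor excluded.

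**3. Does the model turn a level into a change?** Aims 1 and 2 include readiness, so if the ladder is treated as continuous, the linear mixed model in section 5 applies to it. The only structure given is the clinician intercept. Neither that paragraph nor the one on linked patient-provider data has an earlier ladder value, a time term, a change score or a rule for what counts as an advance.

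**4. What a level analysis can show.** For any smoker, later level = earlier level + change. The coefficient of a predictor on the later level is therefore the sum of two parts:

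b(level) = b(earlier level) + b(change)

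With no earlier value in the model, the two parts cannot be separated. b(level) can be non-zero when b(change) is zero, and b(change) can be non-zero when b(level) is zero. The hypotheses concern b(change); section 3.4 as modelled estimates b(level).

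**5. Size.** The power paragraph claims at least 80% power for a standardized coefficient of 0.2 or more and says that the smokers-only subsample was accounted for. It does not give the number of smokers. No section gives a pre-existing difference in readiness between groups or the correlation of ladder values over time. The power figure therefore cannot be turned into a size for this problem, and the point does not depend on it.

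**The case against.** The strongest reply is that the operative definitions agree. The aims, section 3.4 and Table 2 all give a level, and the power paragraph speaks of testing associations. On this view the plan is coherent and *advances* is loose wording for higher readiness. That much stands: a level outcome is legitimate and the planned model suits it. But it concedes that the Summary, Introduction, section 3.1 and both hypotheses claim something the outcome does not measure.

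A second reply is that this is a shortened protocol written after data collection, with procedures and follow-up marked as not applicable. Missing timing is then partly a product of the document type, and the 6-month point leaves room for a repeat ladder. This also stands, and it limits the point. Even so, the hypotheses, the outcome variable, the measures table and the model are all present, and these are the parts that conflict. A repeat ladder would not resolve it, because section 3.4 would still define a level.

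Three stronger readings are tempting and are not supported.

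- A reader might infer that the ladder was given only once. The cross-sectional label points that way, but the document's silence does not establish it.
- A reader might infer that a yes/no advance is planned, because section 5 refers to binary outcomes. Screening completion is binary and explains that text; no section describes a dichotomised ladder.
- A reader might infer that readiness has no planned analysis, because the model-selection sentence names only decision quality and screening completion. The mixed-model sentence covers continuous outcomes of both aims.

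**Conclusion.** The inconsistency is certain from the text: a primary outcome is hypothesised as change and defined as level, and nothing in the analysis section bridges the two. As defined in section 3.4, it supports an association with level of readiness and cannot by itself support the readiness part of Hypotheses 1 and 2 as worded.

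The level analysis is not wrong in itself. It misleads only if reported as advance, and a reader should not infer that the results will be false. No size can be given, since the documents supply none of the inputs that one would need. Whether the remedy is rewording or a new definition depends on a fact that the documents leave open, namely whether the ladder was repeated. The matter should be settled before results are reported; analysis is the only activity still under way.

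**What to change.** State when the ladder was measured, then take one of two routes.

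1. *Measured once, or level is what is meant.* Reword the Summary, Introduction, section 3.1 and both hypotheses to level of readiness, and limit the conclusion to association. The cost is wording and a narrower claim.

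2. *Measured at enrolment and 6 months, and advance is what is meant.* In section 3.4, define the outcome as the 6-month ladder relative to the enrolment ladder among those smoking at enrolment. Keep those who quit by 6 months in the analysis; restricting to people still smoking then would drop smokers who had gone as far as quitting. Add the enrolment value to the mixed model already planned, or analyse a change score. Label the definition as made after data collection. State that it measures change after the discussion: section 4.2.2 requires a discussion within the past month, so the enrolment value already follows it.

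Route 2 needs no new data but carries two costs. It is a post hoc definition of a primary outcome, and adjusting for a value taken after the discussion may remove any immediate effect of the discussion itself.

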2.1. Background/literature review (make sure you provide references)

a. Scientific Background

Provide the scientific or scholarly background for, rationale for, and significance of the research based on the existing literature and how will it add to existing knowledge. A short list of references or bibliography must be included as part of this document, uploaded separately, or provide the relevant page number(s) of the grant where references or bibliography can be found.

Lung cancer kills more people in the U.S. than any other cancer, primarily because most people are diagnosed at an advanced stage where treatment options are limited, and mortality is high. Lung cancer screening is a complex issue because there are associated risks and potential harms including false-positive results, over-diagnosis, and incidental findings that can lead to a cascade of follow-up tests and treatments. The decision to screen for lung cancer is not straightforward and is the epitome of a preference-sensitive cancer screening decision best made in the context of SDM. Multiple professional organizations advocate for SDM in lung cancer screening,^{1,2} and in an unprecedented move, Medicare mandated SDM documentation for screening reimbursement. SDM has been studied in other types of cancer screening but has focused primarily on screening *behavior* as opposed to the decision-making process.

SDM is viewed as the pinnacle of patient-centered care and resonates with the ethical imperative of respect for patient autonomy and engagement.³ Epstein and Street's summary of the evidence on patient-centered communication posits clinical encounters between a patient and clinician should be based upon collaboration and deliberation.⁴ Research advancing the science of SDM has been thwarted primarily because the process of SDM has become somewhat synonymous with patient decision aids. The prevailing belief that information exchange via patient decision aids would enhance the patient-clinician collaborative process has resulted in studies that narrowly focused on the effects of decision aids rather than understanding the causal mechanisms between SDM and patient decisional and behavioral outcomes.⁵ This project focuses on the critical components of SDM and factors associated with positive patient decisional and behavioral outcomes essential to advancing the state of the science in lung cancer screening decisions.

3.1. Study Rationale/Problem Statement/Research question or Study significance

This project specifically seeks to identify the components of patient-clinician discussions about lung cancer screening that contribute to high quality decisions and subsequent important behavioral outcomes (screening completion among patients who decide to screen; stage-of-readiness advancement for smoking cessation among current smokers)

3.2. Hypothesis (if applicable)

Our central hypothesis was that patients who perceive lung cancer screening discussions with their clinician as shared/mutual will have positive decisional and behavioral outcomes. The behavioral outcomes we are evaluating are consistent with recent findings linking lung cancer screening with improved smoking cessation rates.

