Quantitative Data Analysis and Interpretation. Our analyses were being defined *a priori* to address the study aims. We are using descriptive statistics such as means, standard deviations, and frequency distributions to examine data quality, identify patterns of missing and out-of-range values, and evaluate the assumptions of statistical tests. Remediation of normal distribution assumption violations will be accomplished using methods such as Box-Cox family transformations, or other methods as appropriate. Assessment of internal consistency reliability of all scales will be carried out using the Cronbach's alpha coefficient. Continuous outcomes (Aims 1 and 2) will be analyzed based on linear mixed effects models, with a random intercept according to the clinician, to account for the association between patients within the same clinician. Secondary analyses of item level components, consisting of Likert scale data, will be analyzed using Generalized Estimating Equations, which allow for the use of distributions in the Exponential Family other than the Normal Distribution. This will allow for the testing and use of the appropriate probability distribution to be used, while also accounting for the association between patients within the same clinician. Model selection for analyses focused on correlates of decision quality and screening completion will be based on Akaike's Information Criterion (AIC), instead of the usual statistical significance level (to avoid type I error inflation); this approach has been shown to lead to optimized models. We will only consider the statistical significance of each independent variable in the final models if the corresponding overall model test is significant at an alpha=0.05.

Patient-Provider Data Analyses. We are conducting a planned secondary analysis for physicians who have patients who respond to the survey (an estimated 40% of the total number of patients). We will perform a multilevel analysis using a model that contains

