variables from providers and patients nested within those providers. This comparison may be on a 1:1 or 1:many level, depending on how many SDM patients of a given enrolled provider also enroll in the study. These multi-level models will be used to test physician level and patient level variables for their potential significant association with the outcomes. For continuous outcomes a linear link and normal error distribution will be used, and for binary outcomes a logit link and binomial error distribution will be used. The results will be interpreted in terms of the model's coefficients which represent average effects over the sample; therefore, analyses involving linking of patients and providers will protect the providers and patients from being identified.

Data Quality Control. Much of the data collected has been as part of previously validated instruments, yielding high quality data.

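### The central hypothesis is about patient-perceived shared decision-making, but no analysis is tied to it, and AIC selection plus the overall-model gate can leave two of the three outcomes without an unselected estimate

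*Combined protocol and SAP*

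**What the plan says.** The central hypothesis, in Section 1 and again in Section 3.2, is that "patients who perceive lung cancer screening discussions with their clinician as shared/mutual will have positive decisional and behavioral outcomes". The exposure is what the patient perceived.

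Section 3.3 turns the research question into two aims, each with a hypothesis.
- Hypothesis 1 covers clinician factors: "Increased clinician knowledge, positive attitude toward lung cancer screening, positive attitude toward shared decision making (SDM), decreased clinician perceived barriers", plus referral propensity.
- Aim 2 is to "identify patient factors that predict" the three outcomes. Its hypothesis names two factors: "Patient-perceived stigma and medical mistrust predict decreased decision quality, screening completion, and advances in stage of readiness for cessation".

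The SDM-Q-9 appears once, in Section 5.5, Table 2, as the patient-level measure of perceived SDM. It is given no role in the analysis.

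Section 5 (Quantitative Data Analysis and Interpretation) specifies "linear mixed effects models, with a random intercept according to the clinician" for continuous outcomes and lists no fixed effects. It then says: "Model selection for analyses focused on correlates of decision quality and screening completion will be based on" AIC. No term is exempted. The next sentence limits attention to coefficient significance to final models whose overall test reaches 0.05. The Patient-Provider Data Analyses, a secondary analysis, will "test physician level and patient level variables for their potential significant association with the outcomes", again without naming any variable.

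**The concern.** A central hypothesis should lead to a named exposure, a named model and a result that is reported whatever it shows. Here that chain breaks after the hypothesis. The nearest items are not substitutes: the SDM attitude in Hypothesis 1 belongs to the clinician, and the documented SDM discussion (high/low) in Table 2 comes from the EHR.

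Two rules in Section 5 make the gap matter for decision quality and screening completion. If AIC removes the SDM-Q-9, the plan calls for no estimate, interval or test for it. If AIC keeps it, the estimate is seen only because it was large enough to survive, and is biased away from zero. Even when it is kept, its significance is set aside if the overall model test fails. A null or small association would be a real answer to the central hypothesis, and it is the answer this procedure is most likely to leave out.

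**Working it through.** **Text check.** Is patient-perceived SDM named in each place?
- Central hypothesis (Sections 1 and 3.2): yes, as the exposure.
- Hypothesis 1 (Section 3.3): no; five clinician factors.
- Hypothesis 2 (Section 3.3): no; stigma and mistrust.
- Aim 2 (Section 3.3): admitted under a general phrase, not required.
- Table 2 (Section 5.5): yes, as a measure only.
- Main and multilevel models (Section 5): no; no fixed effects are named for any hypothesis.
- AIC rule (Section 5): decision quality and screening completion only; no protected term.

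**The plan's own figure.** The plan gives no number for this point. Its power statement (at least 80%) is for a generic binary predictor with a standardized coefficient of 0.2 or an odds ratio of 2.5. The simulation inputs are not given, and nothing below depends on it.

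**How often would AIC drop the SDM-Q-9? Illustration for decision quality only.**

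Inputs:
- n = 553 patients (Section 5; the Summary has 552, which makes no practical difference).
- Standardized coefficient β = 0, 0.10 or 0.20 (assumed; 0.2 matches the plan's coefficient for a binary predictor).
- R² = 0.3 to 0.5 between the SDM-Q-9 and the other scales (assumed).
- Residual variance 1, linear model, clustering by clinician ignored (assumed).

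AIC keeps a one-parameter term when its likelihood-ratio statistic exceeds 2, that is |Z| > √2 = 1.414. This is equivalent to a significance level of 0.157. With Z ~ N(δ, 1) and δ = β√(n(1 − R²)),

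P(drop) = Φ(1.414 − δ) − Φ(−1.414 − δ).

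- β = 0: δ = 0, P(drop) = 1 − 0.157 = 84%.
- β = 0.10, R² = 0.3: δ = 0.10 × √387.1 = 1.97, P(drop) = 29%.
- β = 0.10, R² = 0.5: δ = 0.10 × √276.5 = 1.66, P(drop) = 40%.
- β = 0.20, R² = 0.3: δ = 3.93, P(drop) = 1%.
- β = 0.20, R² = 0.5: δ = 3.33, P(drop) = 3%.

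**Sensitivity to residual variance.** If the model explained 30% of outcome variance (assumed), residual variance would be 0.7 and δ would be divided by √0.7. At β = 0.10, δ becomes 2.35 and 1.99, and P(drop) falls to 17% and 28%.

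**Simulation check.** Backward AIC was run with 12 candidate covariates at n = 553 and residual variance 1, with 300 data sets per setting. At β = 0 the drop rate was 83–84%. At β = 0.10 it was 18% with uncorrelated covariates and 23% with pairwise correlation 0.3. That correlation gives R² = 11 × 0.3² / (1 + 10 × 0.3) = 0.25, below the 0.3–0.5 range, so a rate under 29% is expected.

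**Size of the selection effect.** At β = 0.10, the average estimate when the term is kept is E(Z | |Z| > 1.414)/δ times the truth: about 1.24 at R² = 0.3 and 1.38 at R² = 0.5.

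**Is the test feasible with the data in hand?** With the term forced in, the smallest partial correlation detectable with 80% power (two-sided 0.05, clustering ignored) is 2.80/√(553 + 2.80²) = 0.118. Three unadjusted tests carry a family-wise error of 1 − 0.95³ = 14.3% if independent.

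**The case against.** The strongest reply is that the SDM-Q-9 is already inside the study. It is a patient-level measure, Aim 2 covers patient factors, and the multilevel models cover patient-level variables. That stands. A reader might infer that the study cannot or will not test its central claim, but the documents support only that the test is permitted and not required.

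The omission is also not peculiar to SDM: Section 5 names no fixed effects, so stigma, mistrust and clinician knowledge are equally unprotected. That stands too, but those variables at least appear in a hypothesis that a report must address. Section 5 does not say outright that hypothesis variables may be removed; this follows from an AIC rule with no exemption.

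A reader might extend the AIC problem to all three outcomes, but the AIC sentence does not name stage of readiness. A reader might also expect much higher drop rates by using the linked patient-provider subset, estimated at 40% of patients. That subset serves a secondary analysis. The SDM-Q-9 and the decision-quality scale both come from the patient survey, so this test does not need linked provider data.

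Finally, AIC rarely loses a strong effect: 1–3% at 0.20. True, but that does not help when the effect is small or absent.

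**Conclusion.** The point holds as a gap in specification, and the plan should be changed. The textual finding is firm: the exposure in the central hypothesis is in neither operational hypothesis and is tied to no analysis. For decision quality and screening completion, the AIC rule and the overall-test gate, followed as written, can leave that hypothesis with no estimate or only a selected one. For stage of readiness the only problem is that no model names the SDM-Q-9.

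The size is less certain. The figures of 84%, 29–40% and 1–3% apply to decision quality under a linear model, with assumed coefficients, assumed overlap among scales, residual variance 1 and no clustering. The middle range falls if the other covariates explain outcome variance. The figures do not carry over to screening completion, which is binary and limited to patients who decide to screen, a number the documents do not give.

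**What to change.** - Add a hypothesis that names the SDM-Q-9 total score as the exposure for each of the three primary outcomes.
- Force it into each model with a fixed adjustment set of patient characteristics already collected, for example from the demographic and health-status items in Table 2. List the set before fitting.
- Report its estimate and 95% CI whatever AIC selects and whatever the overall model test shows. Exempting it from AIC alone would leave the second gate in place.
- Keep AIC for exploratory correlates, and label them so.
- State a multiplicity rule for the three tests.
- Date the change, say that it was added after data collection, and state whether outcome results had been seen.

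The cost is a revision of the analysis text and three forced coefficients; no new data are needed. The downside is three more tests, which cannot be called fully prespecified because the document says that data are collected and analysis is under way.
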